7. STUDY CALENDAR & EVALUATIONS

Cycle = 14 days-28 daysREQUIRED ASSESSMENTSInformed ConsentXMedical history1XPhysical examXVital signs, ECOG Performance status2XECGXQuality of Life assessment (EORTC-QLQ-C30)3AEs & concomitant medicationsAEs & concomitant medicationsXLABORATORY ASSESSMENTSComplete Blood Cell Count with diff (CBC)4-14dCA 19-95XPT/INR and aPTT-14dPregnancy test (serum) WOCBP6-7dDISEASE ASSESSMENTCCT of chest7XCT or MRI of abdomen and pelvis7XMRI Brain7XBone/PET Scan7XTREATMENT EXPOSUREFOLFOXLiposomal IrinotecanCORRELATIVE STUDIES (SPECIMEN COLLECTION)Prior Genetic Sequencing Results8Fresh Biopsy8Blood samples9Elood Samples9Central submission of CT/MRI images ¹⁶ Elood	Day 1 (±3) X X X X X X X X X X X X X X X X X X X	$\begin{array}{c} \text{Day 1} \\ (\pm 3) \end{array}$	30 days post Tx X X X X X X X X X X X	Q 3 months ± 14 days
Informed ConsentXMedical history1XPhysical examXVital signs, ECOG Performance status2XECGXQuality of Life assessment (EORTC-QLQ-C30)3AEs & concomitant medicationsXLABORATORY ASSESSMENTSComplete Blood Cell Count with diff (CBC)4-14dComprehensive Metabolic Profile (CMP)4-14dCA 19-95XPT/INR and aPTT-14dPregnancy test (serum) WOCBP6-7dDISEASE ASSESSMENTCT of chest7XCT or MRI of abdomen and pelvis7XMRI Brain7XBone/PET Scan7XTREATMENT EXPOSUREFOLFOXLiposomal IrinotecanCORRELATIVE STUDIES (SPECIMEN COLLECTION)Prior Genetic Sequencing Results8Fresh Biopsy8Blood samples9	$\begin{array}{c} X \\ X^{3} \\ X \\ \hline X^{13} \\ X^{13} \\ X^{13} \\ X^{13} \end{array}$	$\begin{array}{c c} X \\ \hline \\ Q \ 4 \ cycles^3 \\ X \\ \hline \\ \\ X \\ \hline \\ X \\ \hline \\ X \end{array}$	X X X X X X	
Medical history1XPhysical examXVital signs, ECOG Performance status2XECGXQuality of Life assessment (EORTC-QLQ-C30)3AEs & concomitant medicationsAEs & concomitant medicationsXLABORATORY ASSESSMENTSComplete Blood Cell Count with diff (CBC)4Complete Blood Cell Count with diff (CBC)4-14dComprehensive Metabolic Profile (CMP)4-14dCA 19-95XPT/INR and aPTT-14dPregnancy test (serum) WOCBP6-7dDISEASE ASSESSMENTCT of chest7CT of chest7XMRI Brain7XBone/PET Scan7XTREATMENT EXPOSUREFOLFOXLiposomal IrinotecanCORRELATIVE STUDIES (SPECIMEN COLLECTION)Prior Genetic Sequencing Results8Fresh Biopsy8Blood samples9Blood samples9	$\begin{array}{c} X \\ X^{3} \\ X \\ \hline X^{13} \\ X^{13} \\ X^{13} \\ X^{13} \end{array}$	$\begin{array}{c c} X \\ \hline \\ Q \ 4 \ cycles^3 \\ X \\ \hline \\ \\ X \\ \hline \\ X \\ \hline \\ X \end{array}$	X X X X X X	
Physical examXVital signs, ECOG Performance status2XECGXQuality of Life assessment (EORTC-QLQ-C30)3AEs & concomitant medicationsAEs & concomitant medicationsXLABORATORY ASSESSMENTSComplete Blood Cell Count with diff (CBC)4Complete Blood Cell Count with diff (CBC)4-14dComprehensive Metabolic Profile (CMP)4-14dCA 19-95XPT/INR and aPTT-14dPregnancy test (serum) WOCBP6-7dDISEASE ASSESSMENTCT of chest7CT of chest7XCT or MRI of abdomen and pelvis7XMRI Brain7XBone/PET Scan7XTREATMENT EXPOSUREFOLFOXLiposomal IrinotecanCORRELATIVE STUDIES (SPECIMEN COLLECTION)Prior Genetic Sequencing Results8Fresh Biopsy8Blood samples9Blood samples9	$\begin{array}{c} X \\ X^{3} \\ X \\ \hline X^{13} \\ X^{13} \\ X^{13} \\ X^{13} \end{array}$	$\begin{array}{c c} X \\ \hline \\ Q \ 4 \ cycles^3 \\ X \\ \hline \\ \\ X \\ \hline \\ X \\ \hline \\ X \end{array}$	X X X X X X	
Vital signs, ECOG Performance status2XECGXQuality of Life assessment (EORTC-QLQ-C30)3AEs & concomitant medicationsXLABORATORY ASSESSMENTSComplete Blood Cell Count with diff (CBC)4-14dComprehensive Metabolic Profile (CMP)4-14dCA 19-95XPT/INR and aPTT-14dPregnancy test (serum) WOCBP6-7dDISEASE ASSESSMENTCT of chest7XCT or MRI of abdomen and pelvis7XMRI Brain7XBone/PET Scan7XTREATMENT EXPOSUREFOLFOXLiposomal IrinotecanCORRELATIVE STUDIES (SPECIMEN COLLECTION)Prior Genetic Sequencing Results8Fresh Biopsy8Blood samples9	$\begin{array}{c} X \\ X^{3} \\ X \\ \hline X^{13} \\ X^{13} \\ X^{13} \\ X^{13} \end{array}$	$\begin{array}{c c} X \\ \hline \\ Q \ 4 \ cycles^3 \\ X \\ \hline \\ \\ X \\ \hline \\ X \\ \hline \\ X \end{array}$	X X X X X X	
ECGXQuality of Life assessment (EORTC-QLQ-C30)3AEs & concomitant medicationsX LABORATORY ASSESSMENTS XComplete Blood Cell Count with diff (CBC)4-14dComprehensive Metabolic Profile (CMP)4-14dCA 19-95XPT/INR and aPTT-14dPregnancy test (serum) WOCBP6-7d DISEASE ASSESSMENT CT of chest7CT of chest7XCT or MRI of abdomen and pelvis7XMRI Brain7XBone/PET Scan7X TREATMENT EXPOSURE FOLFOXLiposomal IrinotecanCORRELATIVE STUDIES (SPECIMEN COLLECTION)Prior Genetic Sequencing Results8Fresh Biopsy8Blood samples9Blood samples9		$\begin{array}{c} Q \ 4 \ cycles^3 \\ X \\ \hline \\ X \\ \hline \\ X \\ X \end{array}$	X X X X X	
Quality of Life assessment (EORTC-QLQ-C30)3AEs & concomitant medicationsXLABORATORY ASSESSMENTSComplete Blood Cell Count with diff (CBC)4-14dComprehensive Metabolic Profile (CMP)4-14dCA 19-95XPT/INR and aPTT-14dPregnancy test (serum) WOCBP6-7dDISEASE ASSESSMENTCT of chest7CT of chest7XCT or MRI of abdomen and pelvis7XMRI Brain7XBone/PET Scan7XTREATMENT EXPOSUREFOLFOXLiposomal IrinotecanCORRELATIVE STUDIES (SPECIMEN COLLECTION)Prior Genetic Sequencing Results8Fresh Biopsy8Blood samples9Samples9		X X X X	X X X X	
AEs & concomitant medicationsXLABORATORY ASSESSMENTSComplete Blood Cell Count with diff (CBC) ⁴ -14dComprehensive Metabolic Profile (CMP) ⁴ -14dCA 19-9 ⁵ XPT/INR and aPTT-14dPregnancy test (serum) WOCBP ⁶ -7dDISEASE ASSESSMENT $-14d$ CT of chest ⁷ XCT or MRI of abdomen and pelvis ⁷ XMRI Brain ⁷ XBone/PET Scan ⁷ XTREATMENT EXPOSURE $-14d$ FOLFOX $-14d$ Liposomal Irinotecan $-14d$ CORRELATIVE STUDIES (SPECIMEN COLLECTION)Prior Genetic Sequencing Results ⁸ Fresh Biopsy ⁸ Blood samples ⁹		X X X X	X X X X	
AEs & concomitant medicationsXLABORATORY ASSESSMENTSComplete Blood Cell Count with diff (CBC) ⁴ -14dComprehensive Metabolic Profile (CMP) ⁴ -14dCA 19-9 ⁵ XPT/INR and aPTT-14dPregnancy test (serum) WOCBP ⁶ -7dDISEASE ASSESSMENT $-14d$ CT of chest ⁷ XCT or MRI of abdomen and pelvis ⁷ XMRI Brain ⁷ XBone/PET Scan ⁷ XTREATMENT EXPOSURE $-14d$ FOLFOX $-14d$ Liposomal Irinotecan $-14d$ CORRELATIVE STUDIES (SPECIMEN COLLECTION)Prior Genetic Sequencing Results ⁸ Fresh Biopsy ⁸ Blood samples ⁹		X X X X	X X X	
Complete Blood Cell Count with diff (CBC) ⁴ -14dComprehensive Metabolic Profile (CMP) ⁴ -14dCA 19-9 ⁵ XPT/INR and aPTT-14dPregnancy test (serum) WOCBP ⁶ -7d DISEASE ASSESSMENT -7dCT of chest ⁷ XCT or MRI of abdomen and pelvis ⁷ XMRI Brain ⁷ XBone/PET Scan ⁷ X TREATMENT EXPOSURE	X ¹³ X ¹³	X	X	
Comprehensive Metabolic Profile (CMP)4-14dCA 19-95XPT/INR and aPTT-14dPregnancy test (serum) WOCBP6-7dDISEASE ASSESSMENT-7dCT of chest7XCT or MRI of abdomen and pelvis7XMRI Brain7XBone/PET Scan7XTREATMENT EXPOSURE	X ¹³ X ¹³	X	X	
CA 19-95XPT/INR and aPTT-14dPregnancy test (serum) WOCBP6-7d DISEASE ASSESSMENT XCT of chest7XCT or MRI of abdomen and pelvis7XMRI Brain7XBone/PET Scan7X TREATMENT EXPOSURE FOLFOXFOLFOXLiposomal Irinotecan CORRELATIVE STUDIES (SPECIMEN COLLECTION) Prior Genetic Sequencing Results8Fresh Biopsy8Blood samples9	X ¹³		X X	
PT/INR and aPTT-14dPregnancy test (serum) WOCBP6-7dDISEASE ASSESSMENTCT of chest7XCT or MRI of abdomen and pelvis7XMRI Brain7XBone/PET Scan7XTREATMENT EXPOSUREFOLFOXLiposomal IrinotecanCORRELATIVE STUDIES (SPECIMEN COLLECTION)Prior Genetic Sequencing Results8Fresh Biopsy8Blood samples9	X ¹³	Q 2 cycles ⁵	X	
Pregnancy test (serum) WOCBP6-7dDISEASE ASSESSMENTCT of chest7XCT or MRI of abdomen and pelvis7XMRI Brain7XBone/PET Scan7XTREATMENT EXPOSUREFOLFOXLiposomal IrinotecanCORRELATIVE STUDIES (SPECIMEN COLLECTION)Prior Genetic Sequencing Results8Fresh Biopsy8Blood samples9	-72h			
DISEASE ASSESSMENTCT of chest ⁷ XCT or MRI of abdomen and pelvis ⁷ XMRI Brain ⁷ XBone/PET Scan ⁷ XTREATMENT EXPOSUREFOLFOXLiposomal IrinotecanCORRELATIVE STUDIES (SPECIMEN COLLECTION)Prior Genetic Sequencing Results ⁸ Fresh Biopsy ⁸ Blood samples ⁹	-72h			
DISEASE ASSESSMENTCT of chest7XCT or MRI of abdomen and pelvis7XMRI Brain7XBone/PET Scan7XTREATMENT EXPOSUREFOLFOXLiposomal IrinotecanCORRELATIVE STUDIES (SPECIMEN COLLECTION)Prior Genetic Sequencing Results8Fresh Biopsy8Blood samples9				
CT or MRI of abdomen and pelvis7XMRI Brain7XBone/PET Scan7XTREATMENT EXPOSUREImage: Constant of the second				
MRI Brain ⁷ X Bone/PET Scan ⁷ X TREATMENT EXPOSURE X FOLFOX Liposomal Irinotecan CORRELATIVE STUDIES (SPECIMEN COLLECTION) Prior Genetic Sequencing Results ⁸ Fresh Biopsy ⁸ Blood samples ⁹		Q 4 cycles		
Bone/PET Scan ⁷ X TREATMENT EXPOSURE X FOLFOX Image: Constant of the second state		Q 4 cycles		
Bone/PET Scan ⁷ X TREATMENT EXPOSURE X FOLFOX Image: Constant of the second state				
FOLFOX Liposomal Irinotecan CORRELATIVE STUDIES (SPECIMEN COLLECTION) Prior Genetic Sequencing Results ⁸ Fresh Biopsy ⁸ Blood samples ⁹				
Liposomal Irinotecan CORRELATIVE STUDIES (SPECIMEN COLLECTION) Prior Genetic Sequencing Results ⁸ Fresh Biopsy ⁸ Blood samples ⁹				
CORRELATIVE STUDIES (SPECIMEN COLLECTION) Prior Genetic Sequencing Results ⁸ Fresh Biopsy ⁸ Blood samples ⁹	Х	X		
Prior Genetic Sequencing Results ⁸ Fresh Biopsy ⁸ Blood samples ⁹	Х	X		
Fresh Biopsy ⁸ Blood samples ⁹				
Blood samples ⁹	Х			
			at resection ⁸	
	X ⁹	Q 2 cycles ⁹	X	
Central submission of C 17 when mages			X	
BANKING SAMPLES (SPECIMEN COLLECTION)				
Whole Blood ¹⁰				
Unstained Slides ¹¹ (if available)	X			
Serum and Plasma ¹²	Х			
FOLLOW UP			X	
Survival status, initiation of new anti-cancer therapy	Х		X	

Key to Footnotes

1: Medical History (clinically significant medical history as determined by the treating physician); other data to be obtained includes: diagnosis and staging (pathology report and staging documentation [TNM staging]), smoking history questionnaire and trial awareness question, prior anticancer treatment including medications, [chemotherapy, checkpoint inhibitors, etc.], radiation and surgery.

2: Vital signs to include blood pressure, weight, and height (screening only) and ECOG performance status

3: Assessment of quality of life: prior to treatment on Cycle 1 Day 1 then after every 4 cycles of FOLFOX-nal-IRI (every 8 weeks) and at the safety follow up visit. If a cycle is delayed, QOL assessment should also be delayed. Assessment will be done using the EORTC-QLQ-C30.

4: CMP to include sodium, potassium, chloride, creatinine, blood urea nitrogen; liver function tests (LFTs) to include AST, ALT, total bilirubin, alkaline phosphatase. CBC with differential and platelet count to include WBC, Hgb, ANC and platelet count.

5: CA19-9 will be drawn prior to treatment on Cycle 1 Day 1 then after every 2 cycles of FOLFOX-nal-IRI (that is, every 4 weeks) and at the safety follow up visit. If a cycle is delayed, CA19-9 should also be delayed.

6: For women of childbearing potential (WOCBP): serum β hCG, within 7 days prior to study registration. WOCBP must also have a negative serum pregnancy test within 72 hours of Cycle 1 Day 1.

7: Tumor response will be performed at screening then after every 4 cycles (every 8 weeks); tumor imaging to be done at treatment discontinuation at discretion of investigator. CT pancreas triple phase with pelvis and chest CT may replace the CT chest-abdomen-pelvis if clinically indicated. Baseline bone scan will be obtained if there is any suspicion of metastatic bone involvement. If bone scan is positive at baseline, subjects will be excluded from the study. A screening MRI of brain should be performed to evaluate for the presence of brain metastases as clinically indicated. A CT scan of the brain may be done if MRI is contraindicated. A \pm 7-day window will apply to all imaging.

8: If prior genetic sequencing results were performed as per standard of care, they will be submitted at C1D1. See also Section 8.1. If the subject undergoes surgical resection, tissue will be required from that procedure. All specimens will be used for biospecimen-based research.

9: Research Blood Samples will be collected prior to treatment on Cycle 1 Day 1 then after every 2 cycles (every 4 weeks) starting at Cycle 3 Day 1 of FOLFOX-nal-IRI and at the safety follow up visit. These samples will be used for correlative testing as described in Section 8. See CLM for collection, processing, labeling and shipping instructions.

10: Whole blood for banking is to be collected at Pre-Treatment Cycle 1 Day 1. See CLM for collection, processing, labeling and shipping instructions.

11: Submission of unstained slides for banking from an archived FFPE tumor block (if available). See CLM for collection, labeling, and shipping instructions.

12: Serum and plasma for banking are to be collected at Pre-Treatment Cycle 1 Day 1 and at the 30-Day Safety Follow up visit. See CLM for collection, labeling, processing, and shipping instructions.

13: If screening (baseline) labs were performed within 7 days of Cycle 1 Day 1 of treatment, these do not need to be repeated.

14: When subjects permanently stop study treatment for whatever reason, a safety follow-up visit will occur 30 days (+7 days) after the last dose of treatment or before the initiation of a new anti-cancer treatment, whichever comes first.

15: Subjects without documented disease progression will be followed for disease progression every 3 months for 1 year from Day 30 visit. Once disease progression is documented, subjects will enter a survival follow up period every 3 months from the time of documented progression until death or lost to follow up. This follow up may be accomplished via phone call, email, telehealth, or communication with a local physician.

16: All CT/MRI images obtained throughout the study will be submitted for central analysis at the end of the study.

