1.3.3.1 Safety

The safety data for irinotecan liposome injection are described in detail in the investigator brochure. The most common adverse reactions (≥ 20 %) considered to be related to treatment observed in clinical trials of irinotecan liposome injection in combination with 5-fluorouracil and leucovorin, are: diarrhea, fatigue/asthenia, vomiting, nausea, decreased appetite, stomatitis, and pyrexia. The most common laboratory abnormalities ($\geq 10\%$ Grade 3 or 4) were lymphopenia and neutropenia (ONIVYDE[®] USPI). The most common serious adverse reactions ($\geq 2\%$) of irinotecan liposome injection were diarrhea, vomiting, febrile neutropenia, nausea, pyrexia, sepsis, dehydration, septic shock, pneumonia, acute renal failure and thrombocytopenia

(ONIVYDE[®] European SPC).

The safety of irinotecan liposome injection, a liposomal formulation of irinotecan, may be indirectly compared with the safety of irinotecan, primarily based on a qualitative comparison of adverse reactions reported in the Camptosar[®] US label for irinotecan and in the US Product Label for ONIVYDE[®]. The most common adverse reactions of irinotecan and irinotecan liposome injection are similar and are mainly gastrointestinal events and myelosuppression.

Certain known adverse reactions of irinotecan, including anaphylaxis or anaphylactoid reaction, interstitial lung disease-like pulmonary toxicity, and acute pancreatitis, have not been observed with irinotecan liposome injection to date. This could be due to the limited cumulative patient exposure to date of irinotecan liposome injection, or the use of appropriate premedication and early recognition and treatment of expected adverse events. There is insufficient evidence to know whether these known adverse reactions of irinotecan will eventually be associated with irinotecan liposome injection.

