10.1.7 Adverse Events

Please see the current IB for a detailed list of adverse events. Most common related to Irinotecan liposome injection include hair loss, dizziness, hypomagnesemia, hypokalemia, decreased appetite and decreased weight.

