11. ADVERSE EVENTS

11.1 Definitions

11.1.1 Adverse Event (AE)

An AE is any untoward medical occurrence whether or not considered related to the study drug that appears to change in intensity during the course of the study. The following are examples of AEs:

- Unintended or unfavorable sign or symptom
- A disease temporally associated with participation in the protocol
- An intercurrent illness or injury that impairs the well-being of the subject

Abnormal laboratory values or diagnostic test results constitute AEs only if they induce clinical signs or symptoms or require treatment or further diagnostic tests. Hospitalization for elective surgery or routine clinical procedures that are not the result of an AE (e.g., surgical insertion of central line) should not be recorded as an AE. Disease progression should not be recorded as an AE, unless it is attributable to the study regimen by the site investigator.

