12.2.2 Definition of Secondary Endpoints

- Objective response rate (ORR) as determined by the proportion of subjects with either complete response or partial response as defined by RECIST 1.1 at 8 weeks, 16 weeks, and 24 weeks following initiation of FOLFOX-nal-IRI.
- Stable disease rate (SDR) as determined by the proportion of subjects with no progression of disease as defined by RECIST 1.1, at 8 weeks, 16 weeks, and 24 weeks following initiation of FOLFOX-nal-IRI.
- Rate of resectability as determined by the proportion of subjects who undergo surgical resection of tumors.
- The serum levels of CA 19-9 prior to initiation of chemotherapy and after every 2 cycles (every 4 weeks) following initiation of FOLFOX-nal-IRI.
- Progression-free survival (PFS) as determined by the time interval from the date of first dose of study drug to first documented disease progression or death from any cause, whichever occurs first, if evaluable.
- Overall survival (OS) as defined as the time interval from the date of the first dose of study drug to date of death from any cause.
- Safety and tolerability of FOLFOX-nal-IRI; Grade 3 and 4 toxicities as defined by the NCI Common Terminology Criteria for Adverse Events (NCI CTCAE) v5.

• Quality of life as measured at baseline and after every 4 cycles (every 8 weeks) using the European Organization for Research and Treatment of Cancer Quality-of-Life Core Questionnaire (EORTC-QLQ-C30).

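### Magnesium is not scheduled and the lymphocyte count is not named for capture, so the Grade 3-4 toxicity endpoint may under-count two laboratory effects the protocol itself names

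*Combined protocol and SAP*

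**What the plan says.** Footnote 4 in Section 7 lists the content of the two scheduled blood panels. For haematology it asks for "CBC with differential and platelet count to include WBC, Hgb, ANC and platelet count". For chemistry it begins "CMP to include sodium, potassium, chloride, creatinine, blood urea nitrogen" and adds AST, ALT, total bilirubin and alkaline phosphatase. No row or footnote of the calendar mentions magnesium. ANC is the only component of the differential that the footnote names.

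Two other sections describe what to expect from the drug. Section 1.3.3.1, on nal-IRI with 5-FU and leucovorin, says that the most common laboratory abnormalities (10% or more at "Grade 3 or 4) were lymphopenia and neutropenia"). Section 10.1.7 says that the common effects of the drug "include hair loss, dizziness, hypomagnesemia, hypokalemia, decreased appetite and decreased weight", and gives neither rate nor grade.

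The safety endpoint in Sections 2.2.2 and 12.2.2 is "Grade 3 and 4 toxicities as defined by the NCI Common Terminology Criteria for Adverse Events", version 5. Section 11.1.1 restricts laboratory adverse events: "Abnormal laboratory values or diagnostic test results constitute AEs only if they induce clinical signs or symptoms or require treatment or further diagnostic tests". Section 11.2.1 repeats the restriction by excluding symptom-free abnormalities that need no treatment.

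**The concern.** The endpoint is defined by severity grade, but the plan does not secure the data for two laboratory effects that it names. The gap differs between them.

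- **Magnesium.** No scheduled test exists, so a low value is found only if a site happens to test for it.
- **Lymphocytes.** The value is produced at each scheduled blood count, but nothing says that it is entered in the database. The adverse event rules leave out a low count that causes no symptoms and prompts no treatment or further tests.

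Tolerability is part of the study hypothesis in Section 1.4, and this is a single-arm trial with a target of 28 subjects. Its toxicity table will be read against other reports of the regimen. A low count in that table could reflect how the data were gathered and not how well the drug was tolerated. Differences between sites in local testing would add to this.

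**Working it through.** The plan states no figure on this point, so there is none to reproduce. The check sets the sections side by side and then gives a sense of scale.

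**Step 1. Named effects against the listed analytes**

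| Effect named in the protocol | Where | Matching analyte in footnote 4 |
|---|---|---|
| Neutropenia, Grade 3-4, at least 10% | 1.3.3.1 | ANC, named |
| Lymphopenia, Grade 3-4, at least 10% | 1.3.3.1 | Produced by the differential, not named |
| Hypokalemia, no rate or grade | 10.1.7 | Potassium, named |
| Hypomagnesemia, no rate or grade | 10.1.7 | None |

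In each pair the footnote covers one member and not the other.

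**Step 2. Routes into the Grade 3-4 table**

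- Route A is an adverse event record. Sections 11.1.1 and 11.2.1 admit a laboratory abnormality only if it causes symptoms or needs treatment or further tests.
- Route B is grading the laboratory values directly. Section 12.4 says only that CTCAE version 5.0 will be used to assess safety, and Section 12.6.2 refers back to the endpoint definitions in 12.2.2. Neither says whether grades come from values or from adverse event records.

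A symptom-free, untreated low lymphocyte count fails route A, and route B is not specified. A low magnesium that would have been treated meets the test in route A, but only once someone has measured it.

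**Step 3. Scale for lymphopenia**

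Inputs: n = 28, the target sample size (Section 12.3), and p = 0.10. The latter is the lower bound in Section 1.3.3.1, assumed here to carry over from nal-IRI plus 5-FU and leucovorin to the regimen that also contains oxaliplatin.

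- Expected occurrences = n × p = 28 × 0.10 = 2.8.
- With 25 subjects: 25 × 0.10 = 2.5.
- At an assumed 20%: 28 × 0.20 = 5.6.

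These figures count cases that occur. Let f be the share that are symptomatic, treated or further investigated and so recorded through route A. If adverse event records are the only source, the expected number not recorded is 2.8 × (1 − f). The documents do not give f, so at the 10% rate the result lies anywhere from 0 (f = 1) to 2.8 (f = 0).

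**Step 4. Scale for hypomagnesemia**

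No rate or grade is given, so no expected count can be derived.

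**The case against.** The case on the other side is substantial.

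- **Lymphocytes are measured.** The calendar requires a differential, and Section 14.2 keeps data from calendar procedures done as standard of care in the source documents at least. The database may already have a field for the count; the case report forms are not in the documents. This stands. For lymphocytes the gap is one of naming and grading, and the values could be retrieved.
- **Footnote 4 sets a minimum.** Section 3.1 requires an albumin value at screening although the footnote does not list albumin, so the list is not closed. This stands too, but only the minimum is assured at every site, and for magnesium the minimum is nothing.
- **Experience with this regimen does not point to either event.** Section 1.3.3.1.1 lists related Grade 3 or higher events in 32 subjects at this dose, down to those seen in two subjects, and names neither lymphopenia nor hypomagnesemia. This weakens the 10% assumption. It does not settle the matter, because the section does not say whether that study graded laboratory values directly.
- **Adding analytes alone would change little**, because Sections 11.1.1 and 11.2.1 would still exclude symptom-free, untreated values. This is correct, and the fix must therefore address grading as well.

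A reader might go further and infer that the endpoint cannot contain these two toxicities, or that it will report them as close to zero. The documents do not support that. Section 6 has adverse events of all grades evaluated, the endpoint is not confined to the listed analytes, and symptomatic, treated or investigated cases would be recorded. Nor may the 2.8 expected occurrences be read as 2.8 missed cases.

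**Conclusion.** The concern holds in a limited form. Magnesium is unscheduled, the lymphocyte count is produced but not named for capture, and the adverse event rules exclude symptom-free, untreated laboratory abnormalities. Together these mean that the Grade 3 and 4 endpoint may under-count two effects that the protocol lists as common with nal-IRI.

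The size of the under-count cannot be derived. For lymphopenia, about 2.8 occurrences among 28 subjects rests on an assumed 10% rate taken from a different combination, and an unknown part of these would be recorded anyway. For hypomagnesemia the documents give no rate and do not describe it as a Grade 3 or 4 event. The loss is permanent only for magnesium, since a value never measured cannot be added at analysis.

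This is a minor point that does not touch the primary endpoint. It is worth acting on because the remedy is simple.

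**What to change.** Three changes are needed together:

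1. Add magnesium to the chemistry list in footnote 4, on the draws already scheduled.
2. Name the absolute lymphocyte count, from the differential already required, for entry in the EDC.
3. State in Section 12.4 or 12.6.2 that the Grade 3 and 4 laboratory toxicity summary is graded by CTCAE v5 from recorded laboratory values and presented separately from adverse events. Sections 11.1.1 and 11.2.1 can then stay as they are.

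The cost is one more analyte per draw, two EDC fields and a sentence in the statistical section. The lymphocyte count needs no extra test. The downside is that somewhat more laboratory toxicity will be reported, and the report should say that these grades come from values, so that readers do not compare them directly with tables built from adverse event records.
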